## LIST OF ABBREVIATIONS AND DEFINITIONS OF TERMS

Abbreviation or Specialist Term	Explanation
%CV	Coefficient of Variation
AE	Adverse Event
ANOVA	Analysis of variance
AUC	Area under the Concentration Time Curve
AUC ∞	Area under the Concentration versus Time Curve from Time Zero Extrapolated to Infinity
AUC t	Area under the Concentration versus Time Curve from Time Zero to the Last Quantifiable Concentration
BLQ	Below the Level of Quantification
BDRM	Blind Data Review Meeting
BMI	Body mass index
CI	Confidence Interval
CL	Total Body Clearance
C max	Maximum Observed Concentration
C p	Ceruloplasmin
C p C	Ceruloplasmin-bound copper
CRU	Clinical research unit
CSR	Clinical Study Report
CTCAE	Common Terminology Criteria For Adverse Events
Cu	Copper
EC	Enteric-coated
ECG	Electrocardiogram
EOS	End of Study
EC	Enteric coating
ET	Early Termination
F rel	Relative Bioavailability
HIV	Human immunodeficiency virus
ICF	Informed consent form
λ z	Terminal Elimination Rate Constant
MedDRA	Medical Dictionary for Regulatory Activities
Mo	Molybdenum
NCC	Non-ceruloplasmin-bound copper
PD	Pharmacodynamic(s)
PDF	Portable Document Format
PK	Pharmacokinetic(s)
PT	Preferred term
PUF	Plasma ultrafiltrate
QTcF	QT interval corrected using Fridericia's formula
RPL	Richmond Pharmacology Ltd
RTF	Rich-Text Format
SAP	Statistical Analysis Plan
SAS	Statistical Analysis Software

# Statistical Analysis Plan

SD	Standard Deviation
SI	Systeme Internationale
SOC	System Organ Class
SRC	Safety Review Committee
TEAE	Treatment-Emergent Adverse Event
TESAE	Treatment-Emergent Serious Adverse Event
$t_{1/2}$	Terminal Elimination Half-Life
TFLs	Tables, Figures and Listings
$T_{max}$	Time to Maximum Observed Concentration
TPC	Cu-tetrathiomolybdate-albumin tripartite complex with ALXN1840 administration
$V_d$ ( $V_d/F$ )	Apparent Volume of Distribution
WHO-DD	World Health Organisation – Drug Dictionary

## 1. INTRODUCTION

The purpose of this Statistical Analysis Plan (SAP) is to define the variables and analysis methodology to address the study objectives.

The protocol WTX101-HV-106 Amendment 1, dated 05 February 2019 was used to prepare this SAP.

Pharmacokinetic (PK) parameters calculations and statistical analyses will be the responsibility of Richmond Pharmacology Ltd (RPL). Tables, figures, and listings (TFLs) will be produced using Statistical Analysis Software (SAS), Version 9.3 or higher.

## 2. STUDY OBJECTIVES AND ENDPOINTS

### 2.1 Study objectives

The objectives of this study are:

#### Primary

- To evaluate the ALXN1840 PK in Japanese and non-Japanese healthy subjects.

#### Secondary

- To assess the safety and tolerability of ALXN1840 in Japanese and non-Japanese healthy subjects.

#### Exploratory

- To assess dose-proportionality of ALXN1840 PK of the 15 mg and 60 mg doses within each cohort and with combined cohort data;
- To explore PD and biomarkers of ALXN1840 in Japanese and non-Japanese healthy subjects.

### 2.2 Endpoints

#### Primary

- PK parameters calculated based on the measurements of plasma total molybdenum (Mo) concentrations ( $C_{max}$ ,  $AUC_t$ , and  $AUC_{\infty}$ ).

#### Secondary

- Safety assessed by incidence of TEAEs and TESAEs, physical examination, vital sign measurements, clinical laboratory and ECG results.

#### Exploratory

- PK parameters calculated based on the measurements of plasma total molybdenum (Mo) concentrations ( $C_{max}$ ,  $AUC_t$ , and  $AUC_{\infty}$ ).
- Absolute and percent changes of plasma ceruloplasmin (Cp) and copper (Cu) levels (total Cu, Cp, CpC and NCC);
- The NCC level will be corrected for the amount of Cu bound to the TPC ( $NCC_{corrected}$ ).

### 3. TRIAL DESIGN

This is a single-center, open-label, two-single-dose, two-period, parallel group study evaluating PK and safety of ALXN1840 in healthy subjects. Pharmacokinetic parameters will be calculated based on the measurement of plasma total Mo concentration.

Approximately 24 healthy (12 Japanese and 12 non-Japanese), non-tobacco using, adult male and female subjects who complete the study screening assessments and meet all eligibility criteria will be enrolled to allow for a minimum of 20 subjects to complete the study (10 subjects in each cohort).

Cohort 1: Japanese subjects (defined as those subjects whose parents and grandparents are both Japanese and who have spent less than 5 years outside of Japan).

Cohort 2: Non-Japanese subjects.

The study will be conducted at a single site in the UK.

A Safety Review Committee may be used to evaluate the study data for subject safety and make recommendations on dose modification or termination of the study.

#### 3.1 Overall Design

The study has a screening phase (Days -28 to -2), 2 Dosing Periods (Day -1 to Day 11 each), and an end-of-study (EOS) visit.

After completing the screening phase, enrolled subjects will be admitted to an inpatient facility (CRU) on Day -1 for dosing on Day 1 in Dosing Period 1.

Subjects will be then be readmitted to the CRU for Dosing Period 2 dosing, at least 14 days following the 15 mg dose.

Subjects are confined to the CRU from Days 1 to Day 11 for both Dosing Periods and have samples obtained for PK/PD assessments as well as safety evaluations performed (as detailed in Tables 1 and 2 of the trial protocol). Subjects are discharged 10 days after dosing with Period 1 and Period 2 following the 240 hour post dose procedures, unless medically necessary to extend their confinement.

The subjects in each cohort will follow the dosing regimen as follows:

[figure not shown]
Dosing Period	Planned dose
Dosing Period 1	Subjects will receive a single dose of one 15 mg ALXN1840 enteric-coated (EC) tablet at Hour 0 on Day 1 of Period 1 following an overnight fast.
Dosing Period 2	Subjects will receive a single dose of 4 × 15 mg (for a total of 60 mg) ALXN1840 EC tablets at Hour 0 on Day 1 of Period 2 following an overnight fast.

**Table 1: WTX101-HV-106 Study Drug Dosing Periods**

Subjects will return to the CRU 14 days (+2 days) after the 60 mg dose in Dosing Period 2 for the EOS visit with follow-up procedures, and to determine if any AE had occurred since the last study visit. If subjects withdraw from the study early, they will be seen and assessed by the Investigator or designee, whenever possible, to undergo the procedures associated with the EOS visit. Subjects may be replaced at the discretion of the Sponsor.

### 3.2 Duration of Study

The planned study duration for each subject is approximately 56 days; up to 27 days for screening and approximately 29 days for dosing and follow-up.

\* In Dosing Period 1 and Dosing Period 2, subjects will receive 15 mg and 60 mg of ALXN1840, respectively. Subjects will be readmitted to the CRU for Dosing Period 2 dosing after a minimum of 14 days after the 15 mg dose.

\*\* EOS visit to take place 14 days (+2 days) following 60 mg dose of study drug.  
Abbreviations: CRU = Clinical Research Unit; EOS = end of study, PD = pharmacodynamics;  
PK = pharmacokinetics.

**Figure 1: Study WTX101-HV-106 Schematic**

### 3.3 Sample Size

The study sample size is not based on hypothesis testing with statistical considerations. A sample size of 20 subjects (10 subjects in each cohort) has been selected based on practicality and convention for this type of study. Considering potential for subject drop-out of the study, a total of 24 subjects will be enrolled with 12 Japanese and 12 non-Japanese. The between-subject coefficient of variation (CV) in a previous bioavailability study using  $2 \times 30$  mg EC tablets (Study WTX101-102) was 35%, which can be used to approximate the standard deviation (SD). Two cohorts of 10 subjects produce a two-sided 90% confidence interval with a distance from the difference in means to the limits that is equal to 0.271. For example, if the difference of means is zero and the ratio of means is 1, this level of precision corresponds to an interval from 0.76 to 1.31 on the ratio scale.

### **3.4 Randomization and Blinding**

This is an open-label study.

Eligible subjects who meet all inclusion and no exclusion criteria will be assigned unique numbers for enrollment. In order to minimize selection bias in treatment assignment, subjects who are assigned subject numbers will have them assigned consecutively at the point of study drug dosing, in the same order as they have become eligible.

Study subject numbers will not be reallocated once assigned.

In an effort to achieve balance between the number of males and females in Cohorts 1 and 2, the maximum split in either direction will be 60%:40%.

## **4. STATISTICAL ANALYSES**

In general, descriptive statistics for continuous variables will include number of non-missing values (n), arithmetic mean (Mean), standard deviation (SD), median, minimum, and maximum.

Descriptive statistics for PK parameters will include number of observations (n), arithmetic mean (Mean), standard deviation (SD), arithmetic coefficient of variation (%CV), geometric mean, geometric %CV, median, minimum and maximum.

Categorical variables will be summarized using frequency counts and percentages.

For all tables, except PK parameter tables, descriptive statistics for minimum and maximum will be presented with the same decimal digits as the original data, and with 1 more decimal place than the original data for mean and median; SD will be reported with 2 more decimal places than the original data.

PK parameters will be presented as follows in the listing:  $C_{max}$  and  $T_{max}$  will be presented as given in the raw data;  $AUC_t$ ,  $AUC_{\infty}$ ,  $\lambda_z$ ,  $t_{1/2}$ , CL or CL/F, and  $V_d$  or  $V_d/F$  will be presented with 3 decimal places. Special characters (including subscripts) will not be presented in the tables, listings or figures. Descriptive statistics for PK parameters will be presented with decimal places as appropriate for the particular parameter and cohort.

The analyses will be presented by cohort and period. All collected data will be presented in by-subject listings. Listings will be ordered by cohort, period and subject number and will include all randomized subjects. Deviations from this scheme, if any, will be specified in the relevant section.

Baseline will be defined as the last non-missing value among assessments recorded prior to administration of study drug within respective period. Changes from baseline values will be calculated by period as the post-baseline assessment value minus the baseline value. Only observed values from scheduled time points will be used to create summary tables.

Early Termination (ET) visits will be recoded to ET visits where necessary and reported as ET.

Deviations from the planned analyses will be described in the final clinical study report (CSR).

Page layout of the TFLs will be in landscape mode and will be provided in Microsoft Word. Final TFLs will additionally be created as bookmarked PDF. Further details of page layout will be provided in the TFL shell document. Individual RTF files for tables may be provided to assist medical writing. RTF files will not be compiled into a single document.

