#### 8.2.3.2. Safety Review of 12-lead ECGs

All recorded ECG will be reviewed by the Investigator, or qualified designee, and the review findings will be documented in the CRF. If a subject shows an abnormal ECG, additional safety recordings (including the use of 5- or 12-lead Holter equipment) may be made and the abnormality be followed to resolution, if required.

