## 9.4.2. Safety Analyses

All safety analyses will be performed on the Safety Set.

Safety analyses will include an analysis of all AEs, ECGs, clinical laboratory data, physical examinations, and vital sign measurements using descriptive statistics. No inferential statistical analyses are planned on the safety parameters of this study. The incidence of AEs and SAEs will be summarized, by System Organ Class and Preferred Term for each cohort and overall, by relationship to study drug. Adverse events will also be summarized by cohort and overall by severity. Serious AEs and AEs resulting in withdrawal from the study will be listed. Subjects having multiple AEs within a category (eg, overall, System Organ Class, Preferred Term) will be counted once in that category. For severity tables, a subject's most severe event within a category will be counted.

Changes from baseline in vital sign measurements and laboratory assessments (eg, chemistry, cell blood count with differential, and urinalysis) will be summarized by Japanese and non-Japanese (cohort) and dose. CTCAE will be used as a guide to grade laboratory parameter values in conjunction with clinical judgement. Shift tables by cohort will be produced for these laboratory parameters. These tables will summarize the number of subjects with each baseline grade relative to the reference ranges and changes to the worst highest grade assessed post-dose during the study.

The ECG parameters will be measured at the specified time points, including heart rate, PR, RR, QRS, QT, and corrected QTcF intervals. The average of the triplicate ECG readings at the time points collected will be calculated, and changes from pretreatment baseline values will be assessed by each cohort.

All concomitant medications will be coded using the WHO Drug Dictionary, and the frequency and percentage of concomitant medications will be summarized.

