## 4.11.2 Laboratory Data

Clinical laboratory parameters (including chemistry, hematology (including RBC indices and WBC count with differentials), coagulation and urinalysis) will be listed and abnormal parameters will be flagged as high (H) or low (L) according to reference ranges. Absolute (observed) values and changes from baseline (continuous variables) will be summarized for each parameter and scheduled time point by cohort and period. The last lab value will be used for summary analysis if repeated measurements are made at any time point.

For summary statistics, a lab value with "<" will be replaced with a numeric value by removing the "<" sign. In the listings, the values will be displayed as originally reported by the laboratory.

Laboratory parameter values will be graded according to the Common Terminology Criteria for Adverse Events (CTCAE). Shift tables by cohort and by period will be produced for laboratory parameters graded by CTCAE. These tables will summarize the number of subjects with each baseline grade relative to the normal ranges and changes to the worst highest grade assessed post-dose during the period.

Laboratory parameters planned in the study are outlined in Table 10 of the protocol. Any additional parameters collected as part of investigations will be listed only. Laboratory parameters will be presented in SI units, BUN will be converted to SI unit ( mmol/L).

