## 4.11.3 Electrocardiograms

ECG parameters will be measured at the specified time points and will include heart rate, PR, RR, QRS, QT, and corrected QT interval corrected using Fridericia's formula ( $QTcF = QT/RR^{1/3}$ ). The variables will be listed individually.

Three or more replicate measurements are taken at each protocol time point and the arithmetic mean of the evaluable/available measurements will be taken as the measurement to be used for summary statistics. Arithmetic mean values will also be included into the listings.

For ECG variables, the change from baseline will be derived using the arithmetic mean value of each time-point triplicate minus the arithmetic mean of baseline triplicate values.

Absolute (observed) values and changes from baseline in the ECG variables will be summarized by cohort, period and time point.

An outlier analysis will be performed that will summarize the frequency and percentage of subjects who meet any of the following outlier criteria at each visit by cohort and period:

- QT, QTcF interval > 450 msec to ≤ 480 msec
- QT, QTcF interval > 480 msec to ≤ 500 msec
- QT, QTcF interval > 500 msec
- QT, QTcF interval increases from baseline > 30 msec to ≤ 60 msec
- QT, QTcF interval increases from baseline > 60 msec

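### The SAP's scheduled-values-only rule conflicts with its worst-grade laboratory shift tables, and the SAP does not say which governs

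*SAP*

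**What the plan says.** SAP section 4 (Statistical Analyses) sets a general rule: "Only observed values from scheduled time points will be used to create summary tables". The same section also says: "All collected data will be presented in by-subject listings".

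SAP 4.11.2 plans CTCAE shift tables by cohort and period, from baseline grade with "changes to the worst highest grade assessed post-dose during the period". Protocol 9.4.2 plans the same kind of table with "changes to the worst highest grade assessed post-dose during the study". SAP 4.11.2 adds a rule for repeats: "The last lab value will be used for summary analysis if repeated measurements are made at any time point".

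For ECGs, SAP 4.11.3 averages the replicates at each protocol time point. Its outlier rule reads, in part: "An outlier analysis will be performed that will summarize the frequency and percentage of subjects who meet any of the following outlier criteria at each". The unit that this sentence goes on to name is the single visit, so subjects are counted separately for every visit within each cohort and period. It plans no per-subject maximum.

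The protocol expects data outside the schedule. Section 8.2.4 has clinically significant abnormal laboratory tests repeated until they resolve or cease to matter clinically, and permits unscheduled samples for safety. Section 8.2.3.2 says that after an abnormal ECG "additional safety recordings (including the use of 5- or 12-lead Holter equipment) may be made".

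**The concern.** A worst post-dose grade is an extreme over everything measured. A table restricted to scheduled samples gives the worst scheduled grade, which is a different quantity. The samples at risk of being left out are not a random subset: many are taken because a result was abnormal or a safety question arose, so they come from the subjects whose worst grade matters most.

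At stake is whether the planned laboratory shift tables show what protocol 9.4.2 promises. A programmer who follows SAP section 4 to the letter drops the unscheduled values. One who follows the shift-table wording in 4.11.2 keeps them. Both could claim to have followed the plan, and in cohorts of about 12 they could report visibly different tables.

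**Working it through.** The plan gives no figure on this point to reproduce. The check sets text against text, followed by short arithmetic.

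1. **Reach of the general rule.** The SAP section 4 sentence covers summary tables and is not confined to tables by time point. SAP 4.11.2 describes the shift tables as summarizing numbers of subjects, so they fall under the rule on an ordinary reading. Sections 4.11.2, 4.11.3 and 4.14 state no exemption.

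2. **Target of the shift tables.** SAP 4.11.2 and protocol 9.4.2 both ask for the worst grade after dosing, with no limit to time points. They differ on the window (period against study), but the conflict with the general rule is the same in either.

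3. **What is scheduled** (protocol Tables 1 and 2).
 - Post-dose laboratory draws in each period are at 4, 24, 96 and 216 h. The 216 h draw is limited to chemistry and non-fasting safety bloods.
 - The EOS/ET column has no laboratory mark.
 - EOS falls 14 to 16 days after the 60 mg dose: 14 × 24 = 336 h to 16 × 24 = 384 h.
 - The stretch after 60 mg with no scheduled laboratory value is therefore 336 − 216 = 120 h to 384 − 216 = 168 h. Any laboratory value in it is unscheduled.
 - After the 15 mg dose, by contrast, a Day -1 draw for Period 2 follows.
 - Post-dose ECGs are at 4 h, 24 h and EOS.

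4. **Direction of the effect.** Let S be a subject's worst grade over scheduled values and U the worst over valid unscheduled values. The worst grade found is max(S, U) ≥ S. Leaving U out understates the grade when U > S and changes nothing otherwise. The last-value rule works the same way on a worst grade: if a time point has valid grades a and then b, max(a, b) ≥ b.

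5. **Size for one subject.** With 12 per cohort, 1/12 = 8.3 percentage points. With the minimum of 10 completers, 1/10 = 10 points. A hypothetical case: ALT is Grade 1 at the scheduled 216 h draw and Grade 3 on an unscheduled sample two days later (216 + 48 = 264 h). The literal rule gives 0/12 at Grade 3; using all values gives 1/12.

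6. **QTcF.** Outliers are counted per visit from replicate means at protocol time points. Extra replicates at a scheduled time do enter the mean, because SAP 4.11.3 allows three or more. An extra ECG at another time has no cell in the table, even without the general rule. A QTcF above 500 msec seen only there would count as 0/12 rather than 1/12.

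**The case against.** The strongest reply is that the wording in SAP 4.11.2 is specific to the shift tables and can fairly be read as overriding the general sentence. That stands. A reader might infer that the SAP bars unscheduled values from these tables, but the documents do not settle it: they contain two rules and no order of precedence. Nor does the sentence "Deviations from this scheme, if any, will be specified in the relevant section" close the question. It follows the text on presentation by cohort and period and on listing order, and it comes before the scheduled-only rule, so it most naturally concerns layout.

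A reader might also infer that these values vanish, or that no other table shows a subject's worst response. Neither is right. All collected data are listed by subject. Protocol 8.2.4 has clinically relevant laboratory changes recorded as adverse events, and the TEAE severity tables count each subject's most severe event (SAP 4.11.1). The Grade 3 ALT in the example would appear there if judged clinically significant. What remains is that this route depends on the investigator's judgement, whereas the shift tables apply fixed grading criteria.

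It would be too much to say that the most abnormal values arise off schedule. Repeats and extra ECGs often follow a scheduled abnormal value that is already in the table, and the documents do not say that follow-up values usually exceed it. Protocol 2.3.1 places the liver enzyme rises 4 to 10 weeks into daily dosing, while this study gives two single doses. The absence of an EOS laboratory draw is a feature of the schedule, not of the SAP.

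On ECGs, the per-visit count from replicate means is a sound choice, since protocol 8.2.3.1 uses triplicates to reduce variance. A maximum that pooled Holter traces or single recordings with triplicate means would be noisier and could inflate the outlier count. That objection shapes the fix.

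Finally, safety is a secondary, descriptive objective, and the stopping rules in protocol 6.7 rest on related TEAEs rather than on shift tables.

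**Conclusion.** The concern holds as a conflict between two stated rules. If the general rule is applied literally, the worst-grade tables can only stay the same or move towards normal, by 8.3 points per omitted subject in a cohort of 12 (10 points in a cohort of 10). If the shift-table wording prevails, there is no loss. The size rests on two assumptions: that unscheduled values occur, and that at least one exceeds the subject's worst scheduled grade. The documents foresee the former and give no frequency for the latter.

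The QTcF limitation is real but smaller. The per-visit table does what it says and simply has no place for an ECG taken at another time.

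The point affects how safety is reported. It does not touch the primary PK endpoints, dosing decisions or any inference. It should still be settled before database lock, because protocol 9.4.2 already promises the worst grade found after dosing.

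**What to change.** In SAP 4.11.2, state that worst-grade CTCAE shift tables use all valid post-dose values in the period: scheduled, repeat, unscheduled and early termination. State also that the scheduled-only rule and the last-value rule apply only to descriptive summaries by time point. Results that the laboratory invalidates for a technical reason should be left out, since protocol 8.2.4 allows repeats on that ground. Unscheduled values can be assigned to a period by sampling time relative to the two doses, as SAP 4.11.1 does for TEAEs.

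In SAP 4.11.3, keep the per-visit outlier table from replicate means. Add one row set giving each subject's worst post-baseline QTcF category by cohort and period. It should include unscheduled standard 12-lead ECGs, using the mean of replicates where available, excluding Holter recordings and flagging single recordings.

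The cost is a few sentences and a small programming change, with no new data. The downsides are that counts may look slightly less favourable and that unscheduled ECGs without replicates are noisier, hence the flag.
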